6.6 DOSE MODIFICATION

If a dose of IMP is vomited or omitted, the participant should not take the dose later or 2 doses at the next planned dose, and this information has to be recorded in the patient diary and eCRF.

Investigational medicinal product dose omission is allowed in case of severe toxicity and the reason should be documented in the eCRF. Doses omitted for toxicity are not to be replaced after the 14-day treatment period or compensated at the next planned IMP intake during the 14-day treatment period.

Conditions for dose modifications are aligned in [Table 3](#). Please refer to letrozole label information on additional specific contraindications and events requiring use precaution, and instruction of dose modification.

Table 3 - Dose modification for amcenestant arms and letrozole arm

NCI-CTCAE grade	Dose modifications
Grade 1 or 2	No dose adjustment required except for Grade 2 alanine transferase defined as an AESI *
Grade \geq 3	Amcenestant and letrozole should be definitely discontinued. No reintroduction is allowed.

NCI-CTCAE = National Cancer Institute Common Terminology Criteria for Adverse Events.

* See [Section 8.3](#)

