7 DISCONTINUATION OF STUDY INTERVENTION AND PARTICIPANT DISCONTINUATION/WITHDRAWAL

The IMP should be continued whenever possible. Any IMP discontinuation must be fully documented in the eCRF.

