- There may be instances when copies of medical records for certain cases are requested by the Sponsor. In this case, all participant identifiers, with the exception of the participant number, will be redacted on the copies of the medical records before submission to the Sponsor.
- The Investigator will attempt to establish a diagnosis of the event based on signs, symptoms, and/or other clinical information. Whenever possible, the diagnosis (not the individual signs/symptoms) will be documented as the AE/SAE.

Assessment of intensity

The Investigator will make an assessment of intensity for each AE and SAE reported during the study and assign it using NCI-CTCAE v5.0.

An event is defined as "serious" when it meets at least 1 of the predefined outcomes as described in the definition of an SAE, NOT when it is rated as severe.

Assessment of causality

- The Investigator is obligated to assess the relationship between study intervention and each occurrence of each AE/SAE.
- A "reasonable possibility" of a relationship conveys that there are facts, evidence, and/or arguments to suggest a causal relationship, rather than a relationship cannot be ruled out.
- The Investigator will use clinical judgment to determine the relationship.
- Alternative causes, such as underlying disease(s), concomitant therapy, and other risk factors, as well as the temporal relationship of the event to study intervention administration will be considered and investigated.

- The Investigator will also consult the Investigator's Brochure (IB) and/or Product Information, for marketed products, in his/her assessment.
- For each AE/SAE, the Investigator **must** document in the medical notes that he/she has reviewed the AE/SAE and has provided an assessment of causality.
- There may be situations in which an SAE has occurred and the Investigator has minimal information to include in the initial report to the Sponsor. However, **it is very important that the Investigator always make an assessment of causality for every event before the initial transmission of the SAE data to the Sponsor.**
- The Investigator may change his/her opinion of causality in light of follow-up information and send a SAE follow-up report with the updated causality assessment.
- The causality assessment is one of the criteria used when determining regulatory reporting requirements.

Follow-up of AEs and SAEs

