Section 5.1 Inclusion criteria	In I05, "A breast tumor size of at least 10 mm in short axis measured by ultrasound" was replaced by "A breast tumor size of at least 10 mm in greatest dimension measured by ultrasound"	According to AJCC Cancer Staging Manual 8th edition 2017, the size of tumor refers to the greatest dimension.
Section 5.2 Exclusion criteria	E08, "Currently receiving (and unwilling to discontinue) hormone replacement therapy (last dose < 14 days prior to randomization)" was replaced by "Recent use of hormone replacement therapy (last dose ≤ 30 days prior to randomization)"	Discontinuing HRT could have impact on the tumor including analysis of key biomarkers such as Ki67. So the washout duration of HRT should be at least 30 days prior to randomization.
Section 5.2 exclusion criteria	"E16 Men" was deleted.	It's a duplicated information with I10

[figure not shown]
Section # and Name	Description of Change	Brief Rationale
Section 5.2 exclusion criteria; Section 6.5 Concomitant therapy	New exclusion criteria E21 added. And drugs that are potential inhibitors of UGTs are moved to the list of prohibited therapies/medications	To be in line with the IB of SAR439859, drugs that are potential inhibitors of UGTs are added to the exclusion criteria and the list of prohibited therapies/medications.
Section 5.3 lifestyle consideration; Section 6.5 concomitant therapy	The duration of sun protection for patients taking SAR439859 was extended from "during study treatment" to "during study treatment and for at least 5 days after discontinuation of SAR439859"	SAR439859 is expected to be eliminated from plasma after 5 times plasma half-life (approximately 24 hours). So, it is recommended that sun screen should be used during the treatment and at least 5 days after discontinuation of SAR439859.
Section 6.6 Dose modification	Dose modification criteria for SAR439859 and letrozole was modified to not allow any dose modification or reintroduction of study treatment for NCI CTCAE Grade ≥ 3 AEs.	There is no justification to re-challenge SAR439859 or letrozole to a patient after the first occurrence of Grade ≥ 3 AE considering the short period of treatment (ie, 14 days) while in addition no direct benefit is intended to the patient in this study.
Section 8.3 AE and SAE	"symptomatic overdose has to be reported as a standard AE." replaced to "asymptomatic overdose has to be reported as a standard AE."	Error correction

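### Protocol 6.6 permits dose omission for severe toxicity; if severe means Grade 3 or higher, this conflicts with the stop-and-do-not-reintroduce rule in Table 3 of the same section

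*Protocol*

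**What the plan says.** Protocol 6.6 gives two instructions about toxicity.

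- **The prose.** "Investigational medicinal product dose omission is allowed in case of severe toxicity", with the reason recorded in the eCRF. Doses omitted for toxicity are not replaced after the 14 days "or compensated at the next planned IMP intake during the 14-day treatment period".
- **Table 3.** The section introduces it with the words "Conditions for dose modifications are aligned in". At Grade 1 or 2 it requires no adjustment, apart from Grade 2 ALT. At Grade 3 or higher: "Amcenestant and letrozole should be definitely discontinued. No reintroduction is allowed".

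Four other places bear on how these are read.

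- Protocol 8.3 handles ALT of Grade 2 or higher by discontinuation.
- Protocol 7 opens with a general rule: "The IMP should be continued whenever possible".
- Protocol 10.3 has the investigator rate intensity and "assign it using NCI-CTCAE v5.0". It separates seriousness from intensity by saying that an event is not serious merely because of its intensity ("NOT when it is rated as severe"). It maps *severe* to no grade.
- The Amendment 01 entry for Section 6.6 (Protocol 10.15) gives the reason for the Grade 3 rule: "There is no justification to re-challenge SAR439859 or letrozole to a patient after the first occurrence" of a Grade 3 or higher event, given the short treatment and the absence of intended benefit.

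**The concern.** A site with a patient who has a Grade 3 event on, say, Day 6 can find two answers in one section. Table 3 says stop for good. The prose says that a dose may be omitted for severe toxicity, and its next sentence assumes that a later intake may be planned. The opening line of Section 7 leans the same way.

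This is a stopping rule in a trial that, by Protocol 2.3, offers the patient no direct benefit. Resuming the drug after a Grade 3 or higher event is what Table 3 is there to prevent. If it happened, the planned outputs might not show it. SAP 2.2 tabulates it only if it is classed as a major or critical deviation, and no planned table sets dosing dates against the grade and onset of adverse events.

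**Working it through.** There is no planned figure to reproduce. The check is whether the two instructions can both be followed under each reading of *severe*.

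**Reading 1: severe means Grade 3 or higher.** Table 3 requires permanent discontinuation. A patient who has been permanently discontinued has no next planned intake, so a permission to omit doses with a later intake in view has nothing to apply to. The instructions conflict. This is the natural reading, because NCI-CTCAE grade is the only intensity scale in the protocol and 10.3 uses *severe* as an intensity rating. It remains an assumption.

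**Reading 2: severe means something below Grade 3.** There is no strict contradiction, because Table 3 says only that adjustment is not required at Grade 1 or 2. But the permission then matches no row of Table 3, and the one Grade 2 exception, ALT, leads to discontinuation under 8.3 and not to omission. The site still cannot tell from 6.6 when omission for toxicity applies.

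**Reading 3: withhold while the event is confirmed, then stop.** This fits Table 3. The protocol does allow an interval before discontinuation: 7.1.1 has definitive discontinuations recorded once confirmed, and 8.3 asks for confounders to be excluded first for raised ALT and for photosensitivity. However, 6.6 does not limit the permission to that interval, and the reference to a next planned intake fits it poorly.

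**Which instruction should give way.** Table 3 is graded, explicit and named by 6.6 as the place where the conditions are set. The Amendment 01 rationale confirms its intent. That entry is used here for intent only; the conflict lies wholly in current text.

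**What existing reporting would show.**

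- Protocol 9.4.2.1 plans summaries of adverse events leading to dose modification. SAP 2.4.6.1 carries forward those leading to discontinuation and to dose reduction, not to omission.
- SAP 2.4.4 counts patients with omissions, where an omission is a zero dose between two non-zero doses. That captures resumption after a gap, but not its relation to a Grade 3 event. It also misses a patient who keeps dosing through such an event without a gap, which is the plainest breach of Table 3.

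**What is not affected.** Membership of the mITT population (SAP 2.3.2) needs one dose taken and two biopsies with Ki67 values. Protocol 7.1.1 keeps the post-treatment biopsy on schedule after discontinuation, and 8.6.1 says that omission does not shift the biopsy window. The primary model in SAP 2.4.5.1.1 has no dosing term.

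**The case against.** The strongest reply is that the text largely resolves itself. *Severe* has no grade. The prose permits omission and nowhere says that dosing may restart. The sentence about the next intake is a ban on make-up doses for any toxicity. Table 3 follows directly and forbids reintroduction, and an ungraded permission does not override a graded prohibition beside it. The opening line of Section 7 is general and yields where Table 3 forbids dosing. A hold before discontinuation also has a proper use.

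Most of this stands, and it limits the point. A reader might infer that the protocol tells sites to resume treatment after a Grade 3 event. The documents do not support that: resumption is implied at most, and a site that follows Table 3 will stop. What survives is that 6.6 gives a permission for severe toxicity without saying how it stands to the table beside it. In a safety instruction, that should not be left to the reader.

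A reader might also infer a material effect on the per-protocol analysis. Whether stopping or resuming changes a patient's per-protocol status depends on how SAP 2.3.3 counts days of treatment, which it does not define. That question arises with any missed dose and would remain after 6.6 was corrected, so it is a separate matter and no part of the size of this one.

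**Conclusion.** The point holds conditionally and is minor. If *severe* means Grade 3 or higher, the prose of 6.6 and Table 3 conflict, and the prose is what needs correcting. If it means a lower grade, there is no contradiction, only a permission with no matching row.

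The consequence is confined to the safety of any patient who was dosed after a Grade 3 or higher event, and to the exposure and discontinuation figures for that patient. The documents give no rate of such events, so no number of patients is claimed. The mITT analysis is unaffected. SAP 2.4 records that enrollment ended early and that no hypothesis test will be done on the primary endpoint; with 14 days of treatment per patient, the practical effect is small.

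**What to change.** **Protocol 6.6.** Delete the permission to omit doses for severe toxicity. Alternatively, limit it to: *IMP may be withheld while a suspected Grade 3 or higher event is being confirmed; once confirmed, discontinue permanently per Table 3.* Add no new permission for Grade 1 or 2 events. Table 3 requires no adjustment there apart from ALT, and wider omission would lower exposure in a 14-day pharmacodynamic trial.

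**Study report.** List every patient with any IMP dose taken after the onset date of a Grade 3 or higher adverse event, whether or not a dose was omitted. Do not build the listing on the SAP 2.4.4 omission definition, which misses uninterrupted dosing. A listed patient is a case to review and not automatically a breach, since a dose may have been taken before the grade was known.

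**Cost.** One sentence in the protocol, which helps care only if a patient is still on treatment, and one listing from dosing and adverse event data already collected. No SAP definition changes.

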6.7 INTERVENTION AFTER THE END OF THE STUDY

There is no access to intervention after the end of the study.

7 DISCONTINUATION OF STUDY INTERVENTION AND PARTICIPANT DISCONTINUATION/WITHDRAWAL

The IMP should be continued whenever possible. Any IMP discontinuation must be fully documented in the eCRF.

7.1 DISCONTINUATION OF STUDY INTERVENTION

7.1.1 Definitive discontinuation

The duration of study intervention is 14 days. Participants may withdraw from study treatment if they decide to do so, at any time and irrespective of the reason, or this may be done at the discretion of the Investigator. All efforts should be made to document the reason(s) for discontinuation and this should be documented in the eCRF. If study intervention is permanently discontinued, the participant will remain in the study to be evaluated for safety.

Handling of participants after definitive intervention discontinuation

If the participants withdraw from study treatment before completing 14-day period, they will be requested to get back to the study sites as per planned visit dates after discontinuation. As an example, a participant who discontinues treatment on Day 6 will come to site for planned visits on Day 7 and Day 14. All procedures pre-scheduled for these Day 7 and Day 14 visits will be performed except PK sampling and ECG. If the participants have received less than 70% of planned dose (ie, less than a total of 10 days of treatment), the breast ultrasound will not be performed either. The post-treatment core-cut biopsy sampling from surgery specimen or a new core-cut biopsy will be performed as scheduled.

All participants will be requested to participate in the post-treatment safety follow-up visit (30 [\pm 7] days after last IMP intake).

Participants will be followed-up according to the study procedures specified in this protocol up to the scheduled date of study completion, or up to recovery or stabilization of any AE to be followed-up as specified in this protocol, whichever comes last.

All cases of definitive intervention discontinuation must be recorded by the Investigator in the appropriate pages of the e-CRF when considered as confirmed.

7.2 PARTICIPANT DISCONTINUATION/WITHDRAWAL FROM THE STUDY

- A participant may withdraw from the study at any time at her own request, or may be withdrawn at any time at the discretion of the Investigator for safety, behavioral, compliance, or administrative reasons. This is expected to be uncommon.
- The participant will be permanently discontinued both from the study intervention and from the study at that time.

- If the participant withdraws consent for disclosure of future information, the Sponsor may retain and continue to use any data collected before such a withdrawal of consent.
- If a participant withdraws from the study, he/she may request destruction of any samples taken and not tested, and the Investigator must document this in the site study records.

Participants who withdraw from the study intervention before Day 14 should be explicitly asked about the contribution of possible AEs to their decision, and any AE information elicited must be documented.

All study withdrawals should be recorded by the Investigator in the appropriate screens of the e-CRF and in the participant's medical records. In the medical record, at least the date of the withdrawal and the reason should be documented.

In addition, a participant may withdraw his/her consent to stop participating in the study. Withdrawal of consent for intervention should be distinguished from withdrawal of consent for follow-up visits and from withdrawal of consent for non-participant contact follow-up, eg, medical record checks. The site should document any case of withdrawal of consent.

Participants who have withdrawn from the study cannot be re-randomized/reallocated (treated) in the study. Their inclusion and intervention numbers must not be reused.

7.3 LOST TO FOLLOW UP

A participant will be considered lost to follow-up if he or she repeatedly fails to return for scheduled visits and is unable to be contacted by the study site.

The following actions must be taken if a participant fails to return to the clinic for a required study visit:

- The site must attempt to contact the participant and reschedule the missed visit as soon as possible and counsel the participant on the importance of maintaining the assigned visit schedule and ascertain whether or not the participant wishes to and/or should continue in the study.
- Before a participant is deemed lost to follow up, the Investigator or designee must make every effort to regain contact with the participant (where possible, 3 telephone calls and, if necessary, a certified letter to the participant's last known mailing address or local equivalent methods). These contact attempts should be documented in the participant's medical record.
- Should the participant continue to be unreachable, he/she will be considered to have withdrawn from the study.
- Discontinuation of specific sites or of the study as a whole are handled as part of Appendix 1 ([Section 10.1.9](#)).

8 STUDY ASSESSMENTS AND PROCEDURES

Study procedures and their timing are summarized in the SoA ([Section 1.3](#)). Protocol waivers or exemptions are not allowed.

- Adherence to the study design requirements, including those specified in the SoA, is essential and required for study conduct.
- All screening evaluations must be completed and reviewed to confirm that potential participants meet all eligibility criteria. If the participant fails to meet the exclusion criteria related to laboratory assessments at Screening, the laboratory assessments may be performed one more time to assess eligibility.
- Repeat or unscheduled samples may be taken for safety reasons or for technical issues with the samples.
- Additional safety tests (eg, ECG, hematology, coagulation, and clinical chemistry) can be performed whenever clinically indicated.
- The date of surgery should be fixed before randomization takes place. The time between first IMP administration and surgery should be of 14 days. Surgery should be done 1 day after the last IMP administration; however this could exceptionally be extended to a maximum of 48 hours after the last IMP administration. In case of a longer unexpected surgery delay (>48 hours from last IMP administration), all efforts should be done to perform a tumor biopsy no more than 48 hours of last IMP administration.
- The IMP dose will be taken on-site after fasting tests and pre-dose assessment on Day 1 and Day 14.
- For a regional or national emergency declared by a governmental agency, contingency measures are included in Appendix 14: Contingency Measures for a regional or national emergency that is declared by a governmental agency.

8.1 EFFICACY ASSESSMENTS

8.1.1 Pathological complete response

Pathological Complete Response (pCR) results will be collected from the local pathologist's report following examination of tissue (breast and nodes) removed at the time of surgery and reported in eCRF.

pCR is defined as ypT0N0 or ypTisN0: No histologic evidence of invasive tumor cells in the surgical breast specimen and axillary nodes after neoadjuvant treatment. (Eighth Edition AJCC Cancer Staging Manual; [15]).

8.1.2 ECOG response

Eastern Cooperative Oncology Group (ECOG) response is to be measured according to ECOG response criteria (14) (based on breast tumor shrinkage, pCR and ECOG performance status) by the investigator after a 14-day treatment period.

Tumor size will be measured using breast ultrasound at screening and on Day 14. At screening, tumor size assessment will be used for inclusion criteria and baseline value.

See Appendix 11 ([Section 10.11](#)) for details.

8.1.3 Preoperative Endocrine Prognostic Index (PEPI)

PEPI score will be assessed after a 14-day treatment period. The assessment includes relapse-free survival (RFS) risk score and breast cancer specific survival (BCSS) risk score.

The total PEPI score is the sum of the risk points derived from the pathological tumor (pT) stage, the pathological node (pN) stage, Ki67 levels and ER status (Allred score) of the surgical specimen. The pT and pN will be assessed locally. The Ki67 and ER status will be assessed centrally.

See Appendix 12 ([Section 10.12](#)) for details.

8.2 SAFETY ASSESSMENTS

Planned time points for all safety assessments are provided in the SoA ([Section 1.3](#)).

8.2.1 Physical examinations

- A complete physical examination will include, at a minimum, assessments of the Cardiovascular, Respiratory, Gastrointestinal and Neurological systems. Height (at screening only) and weight will also be measured and recorded.
- Performance status as measured by the ECOG ([Appendix 10 \[Section 10.10\]](#)).
- Investigators should pay special attention to clinical signs related to previous serious illnesses.
- Any new finding or worsening of previous finding should be reported as a new AE.

8.2.2 Vital signs

- Temperature, pulse rate, and blood pressure will be assessed at the time points defined in the SoA ([Section 1.3](#)).

8.2.3 Electrocardiograms

- Standard 12-lead ECGs are recorded after at least 10 minutes in supine position using an electrocardiographic device.

- Single 12-lead ECGs (safety ECGs) will be recorded at screening (locally assessed).
- Triplicates (3 12-lead ECGs) will be recorded within 5 minutes with at least 1 minute between 2 replicates on Day 1 and Day 14 in accordance with the SoA ([Section 1.3](#)), and can be repeated as clinically indicated.

Each ECG consists of a 10-second recording of the 12 leads simultaneously, leading to:

A single 12-lead ECG (25 mm/s, 10mm/mV) printout with heart rate, PR, QRS, QT, QTc automatic correction evaluation (by the ECG device), including date, time and number of the participants, signature of the research physician, and at least 3 complexes for each lead. The Investigator's medical opinion will be recorded in the eCRF. This printout will be retained at the site. ECGs will also be digitally stored to enable further reading by an ECG Core laboratory.

